14.2 Adverse Events

An adverse event (AE) is defined as any untoward medical occurrence associated with the use of a drug in humans, whether or not the event is considered drug-related (21 CFR 312.32 (a)). All AEs will be coded using the MedDRA Version 23.0.

Treatment-emergent adverse events (TEAEs) are defined as any event that occurs or worsens on or after the day that study treatment is initiated. It is not anticipated that any AEs will occur before treatment. However, if in the unlikely event an AE which begins prior to treatment is recorded in the eCRF, the AE will not be included in the summary tables but will be included in the AE data listings.

Severity of an AE is defined as a qualitative assessment of the degree of intensity of an AE as determined by the Investigator or reported to him/her by the subject. The assessment of severity is made irrespective

[REDACTED]

[REDACTED]

[REDACTED]

of relationship to study drug or seriousness of the event and should be categorized with possible values: "Mild", "Moderate", or "Severe".

The relationship of each AE to the study drug should be determined by the Investigator with possible values: "Definitely Related", "Potentially Related", and "Not Related".

Definitely and potentially related TEAEs are considered treatment-related TEAEs.

Drop instillation-related AEs are AEs that are determined by the investigator to be related to the instillation of the study drug.

An overall summary will be presented that includes the number of events and the number and percentage of subjects who experienced at least one TEAE by treatment arm and over all subjects. This summary will also include breakdowns of TEAEs further categorized as ocular or non-ocular; treatment-emergent serious adverse events (TE-SAEs) for ocular, non-ocular, and combined; TEAEs by maximal severity; treatment-related TEAEs by relatedness; drop instillation-related TEAEs; TEAEs leading to premature treatment discontinuation; TEAEs leading to temporary treatment discontinuation; and TEAEs leading to death.

Ocular and non-ocular TEAEs will be summarized using discrete summary statistics and presented by treatment arm at the subject and event level by SOC and PT. If a subject reports the same PT multiple times, that PT will only be counted once within that SOC. As with the PT, if a subject reports multiple conditions within the same SOC, that SOC will only be counted once. In the summary, SOCs will be summarized in ascending alphabetical order; PTs will be listed in order of descending frequency for all subjects within each SOC.

Separate summaries will be provided for the following categories of TEAEs:

- Ocular TEAEs by SOC and PT
- Non-ocular TEAEs by SOC and PT
- Ocular TEAEs by SOC, PT, and Maximal Severity
- Non-ocular TEAEs by SOC, PT, and Maximal Severity
- Ocular Treatment Related TEAEs by SOC and PT
- Non-ocular Treatment Related TEAEs by SOC and PT
- Ocular TEAEs by SOC, PT, Maximal Severity, and Strongest Relationship to Study Drug
- Non-ocular TEAEs by SOC, PT, Maximal Severity, and Strongest Relationship to Study Drug
- TEAEs That Led to Premature Treatment Discontinuation
- TEAEs that Led to Temporary Treatment Discontinuation
- Treatment-emergent SAEs

Summaries of TEAEs by maximal severity will be presented for ocular AEs and non-ocular AEs separately. The number of subjects with any TEAEs (along with percentages) will be tabulated by SOC and PT within

each SOC by treatment arm. To count the number of subjects with any TEAEs, if a subject has multiple TEAEs coded to the same PT, the subject will be counted once under the maximal severity.

All AEs and TEAEs will be presented in a subject listing. TEAEs that led to premature treatment discontinuation, TEAEs that led to temporary treatment discontinuation and AEs that led to study discontinuation will be listed separately. SAEs will be presented in a separate listing. In addition, a separate listing will be generated for drop instillation-related AEs.

As described in [Section 2.7](#), tables, and listings for adverse events with a start date during the on-treatment interval will be generated after Milestone 1. These tables and listings will use all available data and thus, adverse events with start dates during the on-treatment interval and end dates after Day 43/57 will be shown in Milestone 1 tables and listings. After the completion of Milestone 2, the adverse events listings, and the on-treatment interval tables will be re-run to include the Day 90/post-treatment interval data. Additionally, separate tables for adverse events with start dates during the post-treatment interval will be generated for Milestone 2.

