#### 8.3.4 TIME PERIOD AND FREQUENCY FOR EVENT ASSESSMENT AND FOLLOW-UP

The occurrence of an AE or SAE may come to the attention of study personnel during study visits and interviews of a study participant presenting for medical care, or upon review by a study monitor. At study visits, study personnel should pose general questions to the participant to ascertain if the participant experienced any issues prior to the visit.

All AEs, including local and systemic reactions not meeting the criteria for SAEs, will be captured on the appropriate eCRF. Information to be collected includes event description, date of onset, clinician's assessment of severity, relationship to study product (assessed only by those with the training and authority to make a diagnosis), and date of resolution/stabilization of the event. All AEs occurring while in the study must be documented appropriately regardless of relationship.

Any medical condition that is present at the time that the participant is screened will be considered as Baseline and not reported as an AE. However, if the study participant's condition deteriorates at any time during the study, it will be recorded as an AE.

Changes in the severity of an AE will be documented to allow an assessment of the duration of the event at each level of severity to be performed.

The investigator or designee will record all reportable events with start dates occurring any time after study drug is first administered until 7 (for non-serious AEs) or 30 days (for SAEs) after the last day of study participation. At each study visit, the investigator will inquire about the occurrence of AE/SAEs since the last visit. Events will be followed for outcome information until resolution or stabilization.

Whenever possible, recognized medical terms should be used when recording AEs. Colloquialisms and/or abbreviations should not be used. Only one medical concept, preferably a diagnosis instead of individual symptoms, should be recorded as the event (e.g., record congestive heart failure rather than dyspnea, rales and cyanosis). However, if a constellation of signs and/or symptoms cannot be medically characterized as a single diagnosis or syndrome at the time of reporting, each individual sign or symptom should be recorded as a separate AE. A diagnosis that is subsequently established should be reported as follow-up information.

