8.2 Missing or Inconclusive Data Handling

Missing data due to intercurrent events will be handled as per [Section 2.6](#). For the primary analysis, missing data due to lack of efficacy or AEs will be imputed as failures, and missing data without withdrawal or withdrawal due to reasons other than lack of efficacy or AEs will be imputed employing MI using randomized treatment-based MCMC methodology and is further explained in [Section 13](#).

Partial/missing start and end dates for AEs and concomitant medications will be imputed as follows:

Partial/missing start date:

- Dates with missing day only will be imputed as the 1st of the month unless the month and year are same as the month and year of first dose of study medication, in which case missing day will be imputed as the first dose day of study medication.
- Dates with both day and month missing will be imputed as 1 Jan unless the year is same as the year of first dose of study medication, in which case missing day and month will be imputed as the first dose day and month of study medication.
- Completely missing dates will be imputed as the first dose date of study medication unless the end date is on or before the first dose date of study medication, in which case missing date will be imputed as 1 Jan of the same year as the end date.

Partial/missing end date:

- Dates with missing day only will be imputed as the last day of the month unless the month and year are the same as the month and year of the last dose of study medication, in which case missing day will be imputed as the last dose day of study medication.
- Dates with both day and month missing will be imputed as 31 Dec unless the year is same as the year of the last dose of study medication, in which case missing day and month will be imputed as the last dose day and month of study medication.
- If the ongoing flag is missing or “Yes” then the date will not be imputed unless death date is available, in which case the missing date will be imputed as the death date. If ongoing is “No” then the missing end date will be imputed as the last dose date.
- If the imputed date is after the date of death, then the end date will be set equal to the date of death.

The original dates will be displayed in data listings and the imputed dates will be used in derivations only (study day, treatment-emergence status, etc.).

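### SAP 14.2 counts worsening as treatment-emergent but keeps every adverse event that began before dosing out of the tables; one date rule in SAP 8.2 can have a similar effect

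*SAP*

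**What the plan says.** SAP 14.2 defines a TEAE as "any event that occurs or worsens on or after the day that study treatment is initiated". It continues, "It is not anticipated that any AEs will occur before treatment", and provides that if one is nevertheless recorded with an earlier start, "the AE will not be included in the summary tables but will be included in the AE data listings". Treatment-related TEAEs are the TEAEs rated definitely or potentially related, so an event that is not tabulated as a TEAE cannot appear in the treatment-related tables either. Treatment-related adverse effects are the primary safety endpoint (Protocol 3, SAP 2.1).

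SAP 8.2 sets a completely missing AE start date to the first-dose date "unless the end date is on or before the first dose date of study medication"; in that case the start becomes 1 January of the end date's year. These imputed dates are used to derive treatment-emergence. The same rules apply to concomitant medications.

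Protocol 8.3.4 governs what sites record. A condition present at screening "will be considered as Baseline and not reported as an AE". Later worsening of such a condition is handled differently: "if the study participant's condition deteriorates at any time during the study, it will be recorded as an AE". Sites record reportable events with "start dates occurring any time after study drug is first administered". The same section also requires every AE during the study to be documented, and changes in an AE's severity to be documented so that time at each level can be assessed.

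**The concern.** The definition and the table rule in SAP 14.2 give opposite answers for one kind of event: an AE that starts before the first dose and gets worse after it. A programmer cannot follow both sentences. Protocol 2.3.1 lists ocular irritation, conjunctival hyperemia, discomfort and surface staining among the known risks. Each could be present in the days before Day 1 and then be aggravated by instillation. If the table rule is programmed as written, such a worsening is missing from the TEAE summaries, and from the treatment-related summaries even where the investigator rates it definitely related.

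The SAP 8.2 rule raises a separate question about the first-dose day. SAP 14.2 treats that whole day as on treatment, but the imputation moves an event of unknown start that ended that day to a date before treatment. A short-lived reaction to the supervised first drop would fit that pattern if its start date were missing.

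**Working it through.** The documents state no figure on this point, so the check compares the rules for each kind of event and then gives a scale.

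**Inputs.** TEAE definition and table rule: SAP 14.2. Date imputation: SAP 8.2. Recording rules: Protocol 8.3.4. Gap from Screening to Day 1: up to 14 days, or none when both visits fall on one day (SAP 3.1 and Table 2, footnote a). Planned subjects per arm: 209 randomized, 150 at the minimum sample size (Protocol 9.2, SAP 5).

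**Classification.**

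| Event | By the TEAE definition | In the summary tables |
|---|---|---|
| Present at screening, deteriorates on treatment, entered as a new AE dated at the deterioration | TEAE | Yes |
| Starts between Screening and first dose, does not worsen | Not a TEAE | No (rules agree) |
| Starts in that gap, worsens on treatment, new record dated at the worsening | TEAE | Yes |
| Starts in that gap, worsens on treatment, same record with original start date | TEAE | **No (rules conflict)** |
| Start completely missing, ends before first-dose day | Not a TEAE | No (correct) |
| Start completely missing, ends on first-dose day | May be a TEAE; true start unknown | **No, because the start is imputed as 1 January** |
| Start completely missing, ends after first-dose day | TEAE by imputation | Yes |

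**Does the protocol remove the conflict in the fourth row?** Its baseline rule covers only conditions present when the participant is screened, so an event arising afterwards is not baseline. It says that deterioration is recorded as an AE but does not say how that AE is dated. Its instruction on severity changes points towards following a worsening inside one record, which would keep the pre-dose start. Its reporting window begins at first administration, yet it also requires all AEs in the study to be documented, and SAP 14.2 itself provides for pre-dose records. SAP 2.7 adds to the ambiguity: AE tables are built from start dates in an on-treatment interval that begins at screening, which does not fit a rule that excludes pre-dose starts.

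**The sixth row.** The reporting window in Protocol 8.3.4 starts after first administration. An event that a site recorded, with unknown start and an end on the first-dose day, is therefore at least as likely to have begun after the drop as before it. The imputation nevertheless settles it as pre-treatment.

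**Scale.** Change in an arm's TEAE percentage per omitted subject = 100 × 1/n.

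- n = 209: 100/209 = 0.48 percentage points.
- n = 150: 100/150 = 0.67 percentage points.
- No qualifying event recorded: 0.

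This assumes that all planned subjects are dosed and enter the Safety set. The row for subjects with at least one TEAE falls by this amount only if the omitted event is the subject's sole TEAE; otherwise only the rows for that event are affected. The documents give no count or rate of pre-dose AEs, of their worsening, or of missing start dates, so the number of omitted subjects cannot be estimated.

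**The case against.** The strongest reply is that the protocol closes the main route. Conditions present at screening are baseline, their deterioration is recorded as an AE, and reportable events are those starting after first dose. Read together, these imply that a worsening on treatment is entered with a post-dose start and is tabulated. This largely stands for conditions present at screening, although no dating rule is written. It does not reach an AE that arises after Screening and before Day 1. For subjects with both visits on one day there is essentially no such gap.

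It can also be said that the table sentence was meant only to say where non-emergent records go, with the definition governing a worsened event. That may well be the intent, but the sentence turns on when the AE began and contains no such limit.

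On SAP 8.2, the first dose is supervised by site staff, AEs are reviewed at Day 1 and the onset date is a collected item. A reaction seen in the clinic is the event least likely to lack a start date. That stands as to frequency; it does not make the rule consistent with the definition. It is also true that the other start-date rules in SAP 8.2 lean the other way: a missing day in the first-dose month, or missing day and month in the first-dose year, is set to first dose.

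Finally, the excluded events remain in the AE listings. Slit-lamp shift tables (SAP 14.4) and change from baseline in corneal staining (SAP 14.5) would show some ocular worsening by arm. These limit the consequence but do not replace the TEAE tables.

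A reader might infer that TEAEs are in fact undercounted, or that the loss is larger in the arm that irritates more. The documents support neither: they give no rate from which to show any loss, and nothing on how it would divide between arms.

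**Conclusion.** The inconsistency in SAP 14.2 is real on the face of the text. An AE that starts between Screening and first dose and worsens on treatment in the same record is a TEAE by definition and is excluded by the table rule. The SAP 8.2 rule separately makes an AE of unknown start that ends on the first-dose day pre-treatment, although it may have begun after dosing. Each of these two rules can only remove qualifying events, but SAP date handling as a whole is not biased in one direction.

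The expected effect is minor. It requires a pre-dose AE to be entered with its original start date and to worsen without a new record, or a wholly missing start date combined with an end on exactly the first-dose day. The SAP anticipates no pre-dose AEs, in which case the first route contributes nothing. What is established is a possible small undercount in the tables that serve the primary safety endpoint, at about 0.48 points per omitted subject with 209 per arm. Because SAP 1 gives the SAP's analysis methods precedence over the protocol's, the wording should be settled in the SAP.

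**What to change.** Make both changes before unmasking.

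1. **SAP 14.2.** Restrict the exclusion, for example: *An AE that begins before the first dose and does not worsen on or after the first-dose day is listed only. One that worsens on or after that day is a TEAE and is tabulated at its post-dose severity.*
2. **SAP 8.2, AE start dates.** Apply the 1 January imputation only when the end date is strictly before the first-dose date, so that an event ending on the first-dose day takes the first-dose date as its start. State whether the change also applies to concomitant medications, since they share the rule and their classification could change.

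The cost is a few words in two sections and one derivation flag for post-dose worsening. The severity changes that Protocol 8.3.4 already requires to be documented should supply the data, provided that they are dated in the eCRF. The reported TEAE count may be slightly higher, and some events ending on the first-dose day that truly began before the drop would be counted as treatment-emergent.

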**Secondary Endpoints:**

- *Demodex* mite eradication (mite density of 0 mites/lash) from the analysis eye at Day 43.
- Composite cure based on collarette score (0) and erythema score (0) for the upper eyelid of the analysis eye at Day 43.
- Erythema cure based on erythema score (0) for the upper eyelid of the analysis eye at Day 43

Safety will be determined by assessing adverse effects related to the active treatment [REDACTED]

[REDACTED]

**Phase:** 3

**Number of Participants:** Up to 418 participants will be enrolled [REDACTED]

[REDACTED]

**Study Population:** Participants with blepharitis due to *Demodex* infestation defined as having an elevated mite density, collarettes and erythema

**Description of Sites:** Up to 25 sites in the United States

**Description of Study Treatment:** Participants eligible to be randomized will receive one of the following treatments administered bilaterally BID for 43 days: TP-03, 0.25%, or TP-03 vehicle

**Study Duration:** Approximately six months

**Participant Duration:** The study duration for an individual participant is estimated to be approximately three months

**Summary of Visit Schedule:** Screening, Day 1, Day 8, Day 15, Day 22, Day 43, Day 57 [REDACTED] and Day 90. The Day 90 visit should only be conducted at sites that performed specular microscopy.

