3.2 Schedule of Activities

The Schedule of Activities is provided in Table 2.

Table 2. Schedule of Activities

Procedures	Screening Day -14 to 1	Enrollment/initiation of Study Treatment Day 1	Day 8 ± 3 days	Day 15 ± 3 days Day 22 -3/44 days	Day 43 -3/7 days	Day 57 -6/+14 days (Cohort 1 only)	Day 90 ± 14 days (only at sites performing specular microscopy)
Informed consent	X						
Demographics	X						
Medical/ophthalmic history	X						
Concomitant medication review	X	X ^a	X	X	X	X	X
Corrected distance visual acuity (CDVA)	X	X ^a	X	X	X	X	X
Slit lamp biomicroscopy	X	X ^a	X	X	X	X	X
Collarette grading; erythema	X		X	X	X	X	
Corneal staining		X	X	X	X	X	
Intraocular pressure		X			X	X	
Demodex count		X		X	X	X	
Urine pregnancy test ^b	X				X		
Randomization		X					
Dispense study drug; diary		X					
Collection and review of participant diary			X	X			
Collection of study drug and return to participant			X	X			
Adverse event review and evaluation		X	X	X	X	X	X
Collect study drug; diary					X		
Study exit					X ^c	X ^d	X ^e

a: If the Screening and Day 1 visits are completed on the same day, this test does not have to be repeated.

b: Women of childbearing potential

c: Study exit for Cohort 2 subjects if site is not performing specular microscopy

d: Study exit for Cohort 1 subjects if site is not performing specular microscopy

e: Study exit for subjects at sites performing specular microscopy

4. Study Treatments

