7.4 Safety Set

The Safety set will include all randomized subjects who have received at least one dose of study medication. This population will be used to summarize safety variables and will summarize subjects as treated.

8. General Statistical Considerations

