11.2 Concomitant Medications

Concomitant medications will be coded using World Health Organization Drug Dictionary (WHODrug) Global (B3, March 2020) and summarized by therapeutic drug class (Anatomical Therapeutic Chemical [ATC] 4 classification) and preferred name. If the ATC 4 classification is not provided, the next lowest classification that is provided in the coding dictionary will be used. The preferred name will be defined as the active ingredient; if the active ingredient is not provided or includes more than two ingredients (e.g., multivitamins) then the drug name will be summarized as the preferred name.

Concomitant medications are defined as those medications reported as having been taken (1) prior to initiation of study drug administration and continuing for any period of time following the first administration of study drug or (2) at any time following the first administration of study drug.

Concomitant medications will be summarized using the Safety set. Medications will be tabulated for each treatment arm using frequencies and percentages. Subjects may have more than one medication per ATC text. At each level of subject summarization, a subject will be counted once if he/she reports one or more medications. Percentages will be based on the number of subjects in each treatment arm. The ATC classes and preferred names within an ATC class will be sorted in decreasing frequency among all subjects. Listings of concomitant medications will be generated separately for ocular and non-ocular data (as specified by the investigator), including indication, route of administration, start date, and end date or ongoing.

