In addition, a sensitivity analysis will be conducted in which all missing data will be imputed as failure. The difference of proportions test and Fisher's exact test will be used in this sensitivity analysis. Furthermore, the proportion of subjects based on an erythema cure of 0 will be analyzed at all visits in both the analysis and fellow eye, and both the upper and lower eyelid, using observed data only. Stratified analyses will be conducted for the upper eyelid of the analysis eye by site, sex, age group, and race on the FAS using observed data only, unless p-values are not calculable due to sparsity or sample size limitations. In addition, if the COVID-19 Analysis Set consists of $\leq 95\%$ of study subjects, the analysis will be conducted for the upper eyelid of the analysis eye at Day 43 on the COVID-19 Analysis Set with observed data only. These analyses will be conducted using similar SAS® code as described in [Section 13.1.1.3](#).

[REDACTED]

[REDACTED]

[REDACTED]

[REDACTED]

[REDACTED]

[REDACTED]

[REDACTED]

[REDACTED]

[REDACTED]

14. Safety Analyses

All safety analyses will be conducted using the Safety set. Safety analyses will be conducted for each milestone as described in [Section 2.7](#) and in the sections below.

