14.4 Slit-Lamp Biomicroscopy Examination

At each study visit, a slit-lamp biomicroscopy examination will be performed. The following structures will be assessed for pathology defined as normal, abnormal (not clinically significant [NCS]), or abnormal (clinically significant [CS]):

- Cornea
- Conjunctiva
- Anterior chamber
- Iris
- Eyelids and lashes

The results will be summarized using counts and percentages for each treatment arm and for all actively treated subjects at each visit for each eye. Percentages will be based on the number of eyes in each treatment arm with responses. Shift tables for the slit-lamp biomicroscopy parameters will be provided comparing each follow-up visit to baseline. A subject listing of the slit-lamp biomicroscopy parameters will also be produced.

As described in [Section 2.7](#), tables and listings for slit-lamp biomicroscopy examinations will be generated after the completion of Milestone 1 for the on-treatment interval (excluding Day 90) and will be re-run and updated to include Day 90 data after the completion of Milestone 2.

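### Post-treatment AE, medication and procedure percentages are set on the whole Safety set, although only subjects at specular-microscopy sites have scheduled follow-up in that interval, so they will be understated

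*SAP*

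**What the plan says.** SAP 2.7 defines a post-treatment interval running from the Day 43 visit (Cohort 2) or Day 57 visit (Cohort 1) to Day 90, and assigns its safety assessment to Milestone 2. It plans separate tables for AEs, medications and procedures that start in that interval. SAP 11 repeats this for medications and procedures. For AEs, SAP 14.2 says "separate tables for adverse events with start dates during the post-treatment interval will be generated for Milestone 2".

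The population is not narrowed for these tables. SAP 14 states "All safety analyses will be conducted using the Safety set", and SAP 7.4 defines that set: "The Safety set will include all randomized subjects who have received at least one dose of study medication". For medications, SAP 11.2 adds "Percentages will be based on the number of subjects in each treatment arm"; SAP 11.3 has the same rule for procedures. For AEs, SAP 14.2 promises counts and percentages without naming a denominator: "The number of subjects with any TEAEs (along with percentages) will be tabulated by SOC and PT within" each SOC.

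Not everyone is followed through the interval. The protocol synopsis says "The Day 90 visit should only be conducted at sites that performed specular microscopy". In the SAP 3.2 schedule, Day 43 is marked "Study exit for Cohort 2 subjects if site is not performing specular microscopy", and Day 57 is marked the same way for Cohort 1.

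Protocol 8.3.4 adds a reporting tail at all sites. Non-serious AEs are recorded until 7 days, and SAEs until 30 days, after a subject's last day of participation. Protocol 6.5 has medication changes reported throughout the study and gives no tail after exit.

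**The concern.** At sites without specular microscopy, subjects leave the study at the point where the post-treatment interval begins. They have no scheduled visit in it at which AEs or medications would be asked about, yet they stay in the denominator. Unless something is recorded in the short tail, they count as having had no event.

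The SAP avoids this for visit-based measures. For slit lamp, SAP 14.4 says "Percentages will be based on the number of eyes in each treatment arm with responses"; corneal staining (14.5) and pregnancy tests (15.2) are handled likewise. The AE, medication and procedure tables have no such rule.

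What is at stake is the absolute frequency of events after the end of treatment. The fewer the subjects at specular sites, the lower the printed percentage, whatever the drug does.

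**Working it through.** The plan states no post-treatment event rate, no interval-specific denominator and no count of specular sites or subjects, so it has no figure of its own to reproduce. The check is how far the stated denominator pulls a percentage down.

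**Inputs from the documents**
- Interval length: 90 − 43 = 47 days (Cohort 2) and 90 − 57 = 33 days (Cohort 1), using nominal visit days (SAP 2.7, 3.1).
- Recording after exit at other sites: 7 days for non-serious AEs and 30 days for SAEs (protocol 8.3.4); none stated for medications or procedures.
- Planned arm size: about 209 (SAP 5).

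**Assumptions**
- *f*, the share of the Safety set at specular sites, is 0.2 to 0.6. The documents imply only that it is below 1.
- The event rate is constant over the interval and reporting in the tail is complete. Incomplete reporting would make the understatement larger.
- Withdrawals before Day 43/57 are ignored. They also sit in the denominator and would lower the percentages further.

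**Formula**

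Reported % ÷ true % = f + (1 − f) × c, where c is the fraction of the interval in which an event at a non-specular site is still recorded. The fold understatement is the reciprocal.

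- Medications and procedures: c = 0.
- Non-serious AEs: c = 7/47 = 0.149 (Cohort 2) or 7/33 = 0.212 (Cohort 1).
- SAEs: c = 30/47 = 0.638 (Cohort 2) or 30/33 = 0.909 (Cohort 1).

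**Results (ratio, then fold understatement)**

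| Item | f | Cohort 2, 47 days | Cohort 1, 33 days |
|---|---|---|---|
| Medications, procedures | 0.2 | 0.200, 5.0 | 0.200, 5.0 |
| Medications, procedures | 0.6 | 0.600, 1.7 | 0.600, 1.7 |
| Non-serious AEs | 0.2 | 0.2 + 0.8 × 0.149 = 0.319, 3.1 | 0.2 + 0.8 × 0.212 = 0.370, 2.7 |
| Non-serious AEs | 0.6 | 0.6 + 0.4 × 0.149 = 0.660, 1.5 | 0.6 + 0.4 × 0.212 = 0.685, 1.5 |
| SAEs | 0.2 | 0.2 + 0.8 × 0.638 = 0.711, 1.4 | 0.2 + 0.8 × 0.909 = 0.927, 1.08 |
| SAEs | 0.6 | 0.6 + 0.4 × 0.638 = 0.855, 1.17 | 0.6 + 0.4 × 0.909 = 0.964, 1.04 |

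Every ratio is below 1. At f = 0.8 the ratios are 0.80 for medications and procedures, 0.83 to 0.84 for non-serious AEs and 0.93 to 0.98 for SAEs, so the effect shrinks but keeps its direction.

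**In percentages.** Suppose 10% of followed subjects start a new medication in the interval (an assumption for illustration). With f = 0.2, about 42 of 209 per arm are followed and yield 4.2 users; the table shows 4.2/209 = 2.0%. With f = 0.6, about 125 are followed and yield 12.5 users; the table shows 12.5/209 = 6.0%. Dividing by those followed gives 10% in both cases.

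**The case against.** The case against has several parts, and much of it stands as a limit on the point.

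- **Exited subjects are not wholly unobserved.** A reader might apply the 5.0 to 1.7 fold figure to AEs as well. The tail in protocol 8.3.4 does not allow that: the figure fits medications and procedures only, and for SAEs the effect is small. But the tail covers only 7 of 33 to 47 days for non-serious AEs, so it does not remove the problem.
- **The AE denominator is not written down.** SAP 14.2 does not state it; it is inferred from the Safety-set rule in SAP 14, which has no exception for this interval. A programmer following the text would use the whole set. SAP 2.7 does refer to eligible subjects at Milestone 2, but that wording fixes when the milestone is reached, not who is in a table.
- **These are not the only off-drug data.** A reader might infer that they are. In fact SAP 2.7 places Cohort 1 events between Day 43 and Day 57 in the on-treatment tables, subjects who stop drug early stay in the study (protocol 7.1), and the AE listings are re-run at Milestone 2.
- **The extent of follow-up can be found elsewhere.** A reader might say a low rate could not be told apart from absent follow-up. Milestone 2 also re-runs disposition, CDVA and slit-lamp outputs including Day 90, so the number seen can be recovered. It is just not shown beside, or used in, the percentages that depend on it.
- **Both arms are affected alike.** Randomization is blocked by site (SAP 4.1), so the share followed should be similar by arm and the between-arm ratio roughly kept. Nothing in the documents suggests a bias favouring one arm. Absolute percentages and risk differences still shrink.

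**Conclusion.** The point holds as a defect in the denominator of the Milestone 2 post-treatment tables. Followed as written, the SAP understates post-treatment percentages in both arms. The direction follows from the text, given the inferred AE denominator. The size does not, because the share of subjects at specular sites is not in the visible documents.

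For a share of 20% to 60%, a constant event rate and complete reporting in the tail, the understatement is about 5.0 to 1.7 fold for medications and procedures, 3.1 to 1.5 fold for non-serious AEs and 1.4 to 1.04 fold for SAEs. The tables also pool intervals of about 47 and 33 days without saying so.

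The consequence is confined to descriptive safety tables. Efficacy and the on-treatment tables are unaffected.

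**What to change.** In SAP 2.7, 11 and 14.2, base percentages in the post-treatment AE, medication and procedure tables on Safety-set subjects at specular-microscopy sites who had not exited the study by their Day 43 (Cohort 2) or Day 57 (Cohort 1) visit, whether or not they attend Day 90. Requiring a later visit would drop subjects who have an event and do not return.

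Show that number at risk by arm and by cohort in the table header, since the intervals differ (about 47 and 33 days).

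Keep events recorded after exit for subjects at other sites, including SAEs in the 30-day tail, in the same tables as a separate count row without a percentage. These are reports the protocol requires and should not be moved out of the safety tables.

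The cost is SAP wording and one population flag; no new visits or data are needed. The downside is smaller denominators and less favourable percentages. Specular-site subjects who miss Day 90 stay in the denominator, so some dilution can remain.
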